3.1.1 Overview of Trial Periods

This is a first-in-human, Phase 1/2, open-label, multi-center trial to evaluate the safety, tolerability, PK, PD and preliminary efficacy of DYN101 after SAD and MAD in subjects ≥ 16 years of age* with CNMs caused by mutations in *DNM2* or *MTM1* (*for Germany, the subject must be ≥ 18 years of age in accordance with local and national regulations).

Sufficient subjects will be screened in order to ascertain that approximately 18 subjects will be dosed and finish the trial. Subjects may be recruited from an ongoing NHS (Nat-His-CNM Trial Protocol, 2017).

There will be stand-by subjects for replacement of subjects who discontinue the trial early, if needed. Stand-by subjects will perform run-in visits until the last MAD subject has completed Week 13, unless needed for replacement.

The trial will consist of a pre-screening consent, a screening period, a run-in period (if applicable), a SAD part with 4 weeks of follow-up after IMP administration and a washout period of at least 12 weeks (followed by follow-up phone calls until the MAD part starts), a MAD part of 12 weeks, and a MAD extension part of 12 weeks. All subjects will participate in the SAD, MAD and MAD extension parts, unless they withdraw. End of Treatment (EoT) assessments will be performed after 24 weeks of MAD treatment have been completed, i.e. at the Week 25 visit. Subjects will return to the clinic 3 months after the last IMP administration, to follow-up on the subject's status including abnormal laboratory results, AEs, and concomitant medications. The trial design is presented in Figure 1.

Abbreviations: BL: baseline, EoT: End of Treatment, FU: follow-up, MAD: multiple ascending dose, SAD: single ascending dose, SCR: screening, W: week

* All subjects will remain on treatment with weekly IMP administrations and bi-weekly (every 2 weeks) assessments until the last MAD3 subject has completed the MAD Week 25 visit. The data generated from these bi-weekly assessments will not be part of the statistical analysis for this trial (see Section 9.1).

Figure 1: Trial Design: Trial Periods

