4.5 Subject Withdrawal and Trial Termination

It is the investigators responsibility to stop dosing a subject(s) at any stage if they deem it in the subjects' best interest to do so and take any urgent safety measures required to safeguard the subject. Such measures should be reported to the sponsor immediately and to the regulatory authorities or the Independent Ethics Committee/Institutional Review Board (IEC/IRB). Pausing/stopping rules (Section 7.11) should be taken into account.

A subject may be withdrawn from the trial at any time, for any reason, without prejudice to their future medical care by his/her physician or at the institution. Subjects withdrawing from the trial will be encouraged to complete the assessments of the early discontinuation visit, see Section 6.1.5), particularly safety evaluations in the subject's interest and to ensure that data can be recorded in the same way as for subjects who completed the trial. If subjects agree, they will also have the follow-up visit 3 months after their last IMP administration (see Section 6.1.4). Comments (spontaneous or elicited) or complaints made by the subject must be recorded in the electronic case report form (eCRF).

Reasons for withdrawal from the trial may include, but are not limited to:

- For subject's best interest
- SAE
- Any pausing/stopping rule for the trial (as described in Section 7.11)
- Pregnancy
- Protocol violation (except if related to a restriction imposed in response to a pandemic)
- Withdrawal of consent by subject
- Lost to follow-up

In case of temporary IMP discontinuation, it should be discussed with the medical monitor whether continued participation is possible and whether any (pre-) treatment/therapy before resuming IMP administration can be considered useful in order to ensure subject safety. The withdrawal of a subject from IMP by the investigator should be discussed, where possible, with the medical monitor before the subject stops with the IMP. The reason for IMP discontinuation and date of stopping IMP must be recorded on the eCRF and source documents. The total amount of IMP received is registered on the drug accountability form.

Replacement of withdrawn subjects can occur under the circumstances described in Section 3.1.2.

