6.1.3.2 Single Ascending Dose Part

Subjects will receive a single IV administration of DYN101 on Day 1, after which they are followed for 4 weeks up to Day 29.

There will be a subsequent washout period of at least 12 weeks: during Weeks 5-17, subjects will be asked to visit the site every 2 weeks for safety follow-up, even if they do not continue to the MAD part. Where possible, the visits will take place on the same day of the week as the visit on Day 1.

Due to restrictions imposed in response to a pandemic that restrict subject visits, please contact the medical monitor to determine the strategy for continuing the subject in the trial. All efforts must be employed to maintain subject safety. Assessments, if feasible, must be collected during a phone call with the subject. The site should arrange the collection of the blood and urine samples, if at all possible.

Every 2 weeks following the Week 17 visit, subjects will be contacted by phone by qualified site personnel to follow-up on concomitant medications and AEs, until their assigned MAD cohort has been opened.

Subjects who participated in the SAD part will subsequently participate in the MAD part (provided the IDMC has given a favorable advice to proceed, see Section 3.1.1).

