6.1.4 End of Treatment Follow-up Visit

If a subject is NOT continuing on IMP treatment after the trial, the subject will return to the clinic for an EoT follow-up visit 3 months after the last IMP administration, to follow-up on the subject's status including abnormal laboratory results, AEs, and concomitant medications. The follow-up information will be recorded in the eCRF.

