6.1.5 Early Discontinuation

In case subjects are withdrawn from IMP or from the trial, there will be a follow-up visit to query for AEs/SAEs and concomitant medications. In addition, safety, PK and PD/exploratory efficacy assessments may be performed at this early discontinuation visit. The assessments to be performed at this visit correspond to the assessments of the MAD Week 25 visit (excluding IMP administration) (refer to the [TRIAL SCHEDULES](#)). In addition, subjects participating in MAD are encouraged to have a second muscle biopsy taken if the subject had at least 6 weeks of treatment during the MAD part of the trial and discontinued prior to having the Week 13 biopsy obtained; SAD subjects do not need a second muscle biopsy.

If subjects agree, they will also have an EoT follow-up visit 3 months after their last IMP administration.

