7.10 Follow-up on Adverse Events

All AEs and SAEs should be followed until stable, resolved or they have reached a "final outcome" or the subject's participation in the trial ends, whichever comes first.

Adverse events assessed as "related" to IMP and all SAEs and AEs of special interest (regardless of their relationship to IMP) still ongoing after the end of trial participation (i.e. after the follow-up call) should be followed on a regular basis according to the investigator's clinical judgment until the condition is stable.

The outcome "recovering" can be used as the "final outcome" for events that are stabilized (i.e. no further worsening is expected) and expected by the investigator to resolve over time.

The outcome "not recovered" can be used as the "final outcome" for events that are not expected to resolve over time (e.g. cancer).

The outcome "unknown" can be used as the "final outcome" for events for which the outcome is not known.

If a subject dies during the reporting period, attempts should be made to obtain muscle biopsy material to assess muscle histology, ASO concentration, and *DNM2* mRNA.

Follow-up information received after the end of the trial should be sent to the sponsor.

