7.11 Pausing/Stopping Rules

7.11.1 Pausing/Stopping Rules for the Trial

The investigators, together with the medical monitor, will be responsible for the safety monitoring of the trial, and will pause IMP administration in case any of the pre-specified pausing/stopping rules have been met. The sponsor's medical lead will be involved in all discussions and decisions.

If any of the following events occur in any subject in any cohort who received at least one IMP administration in the trial (at any site), the investigator will pause the IMP administration of further subjects in all cohorts and will notify the medical monitor immediately. The medical monitor will inform all the other investigators to pause further IMP administration as well and will notify the IDMC immediately.

- Death in any subject, considered related to IMP; OR
- An anaphylactic reaction within 24 hours of the start of the infusion or the presence of generalized urticaria within 72 hours of the start of the infusion in any subject, considered related to IMP; OR
- An SAE in any subject, considered related to IMP.

Events which would not meet the hospitalization criterion to be reported as an SAE for this trial are:

- Overnight stay for convenience based on the subject/caregiver personal choice
- Overnight stay offered by the investigator based on non-clinical grounds
- For observation of minor reactions which would not on their own warrant admission to hospital, but is preferred in this vulnerable population; OR
- ALT or AST $> 8 \times$ ULN, considered related to IMP and confirmed by repeat testing.

Subjects experiencing any of the events defined above will be permanently withdrawn from IMP administration and will discontinue the trial (see Section 4.5).

Within 3 business days, the IDMC will convene to review the available safety data as outlined in the charter and to discuss further actions (e.g. continue either as planned or with modifications, or to stop the trial). In the event a stopping rule is met, the national authorities will be informed through a substantial amendment. The sites will be allowed to resume activities after the national authorities have received, reviewed, and approved the available safety data and any protocol amendment, if any, and upon receipt of a written notification from the sponsor to allow continued treatment and enrollment.

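### A SAD subject who meets a trial pausing rule must leave the trial, and no text settles whether the two-weekly safety visits to Week 17 continue

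*Protocol*

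**What the plan says.** Protocol 7.11.1 lists four triggers: a related death, a related anaphylactic reaction or generalized urticaria within set times, a related SAE, and a related, confirmed ALT or AST above 8 × ULN. It applies to anyone in any cohort who has had at least one dose, so SAD subjects are included. The consequence is mandatory: "Subjects experiencing any of the events defined above will be permanently withdrawn from IMP administration and will discontinue the trial (see Section 4.5".

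Section 4.5 is softer. It lists "Any pausing/stopping rule for the trial (as described in Section 7.11" among reasons that may lead to withdrawal, and encourages withdrawing subjects to complete the early-discontinuation visit.

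Section 6.1.5 describes that visit: "there will be a follow-up visit to query for AEs/SAEs and concomitant medications". It gives no date, and says other assessments may be done. It then adds: "If subjects agree, they will also have an EoT follow-up visit 3 months after their last IMP administration". Section 6.1.4 is firmer for anyone not continuing IMP: "the subject will return to the clinic for an EoT follow-up visit 3 months after the last IMP administration". The early-discontinuation notes under the two SAD schedules (Baseline and SAD; SAD Follow-up and Washout) repeat the path of encouraged Week 25 assessments and a 3-month visit if the subject agrees.

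Section 6.1.3.2, on Weeks 5 to 17 after the single dose, says that "subjects will be asked to visit the site every 2 weeks for safety follow-up, even if they do not continue to the MAD part". Section 3.1.1 says: "All subjects will participate in the SAD, MAD and MAD extension parts, unless they withdraw".

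Section 7.10 keeps some follow-up alive for related events, SAEs and events of special interest: those "still ongoing after the end of trial participation (i.e. after the follow-up call) should be followed on a regular basis" until stable.

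**The concern.** In the SAD part the single dose has normally been given by the time a pausing rule is met. Stopping IMP protects the subject. Ending trial participation adds no protection and can only remove scheduled monitoring. The protocol already separates the two ideas in 1.5 and 6.1.5, which speak of withdrawal from IMP or from the trial, but 7.11.1 imposes both at once.

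A site that follows 7.11.1 to the letter would stop the two-weekly visits. A site that follows 6.1.3.2 might keep them. On the literal path, the SAD subjects with the most serious related toxicity in a first-in-human trial would have fewer scheduled platelet counts, liver tests and adverse event queries than SAD subjects without it. Thrombocytopenia and impaired hepatic function are both events of special interest in 7.2, so the tests that thin out are relevant ones.

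**Working it through.** No statistical figure is involved. The check compares the text on each path and counts contacts from the Trial Schedules.

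**Step 1: does any text set precedence?** Sections 4.5, 6.1.5 and 7.11.1 and both SAD schedule notes do not mention the two-weekly visits. Section 6.1.3.2 has no exception for subjects who have discontinued. None says whether the discontinuation path replaces those visits or adds to them.

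**Step 2: scheduled visits from Day 29** (SAD Follow-up and Washout schedule)

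- Visits with an adverse event query: Days 29, 43, 57, 71, 85, 99, 113 = 7.
- Platelet counts: the same days = 7, one every 14 days.
- Clinical laboratory tests, which include ALT/AST: Days 29, 57, 85, 113 = 4, one every 28 days. Footnote k can be read to add central biochemistry wherever platelets are counted, which would give 7. So 4 is a minimum.

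**Step 3: the discontinuation path** (MAD Extension schedule, EoT/ED and EoT FU columns)

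- Platelet counts: 1 + 1 = 2 at most.
- Laboratory tests: 1 + 1 = 2 at most.
- Adverse event queries: 1 firm but undated, plus 1 at the 3-month visit.

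**Step 4: the difference, by time of trigger** (discontinuation path at its maximum)

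- Before Day 29: 7 − 2 = 5 fewer platelet counts from Day 29, and at least 4 − 2 = 2 fewer ALT/AST tests (7 − 2 = 5 on the wider reading of footnote k).
- Between Days 29 and 43: 6 visits remain, so 6 − 2 = 4 fewer platelet counts. At least 3 ALT/AST tests remain (Days 57, 85, 113), so at least 3 − 2 = 1 fewer.
- Between Days 71 and 85: 3 visits remain, so 3 − 2 = 1 fewer platelet count.
- After Day 99: 1 visit remains, and the early-discontinuation visit can match it.

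**Step 5: the gap between scheduled checks.** Take 3 months as 90 days, so the 3-month visit is on Day 1 + 90 = Day 91. The protocol does not date the early-discontinuation visit; assume it falls between Day 8 and Day 29. The gap is then 91 − 8 = 83 days down to 91 − 29 = 62 days, apart from 7.10 follow-up of the triggering event.

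**Step 6: exposure in that gap.** Protocol 1.3.1 gives a terminal half-life of 21 days in non-human primates. If it carries over to humans (an assumption), the terminal-phase fraction left is 2^(−28/21) ≈ 40% at 28 days and 2^(−90/21) ≈ 5% at 90 days. Some exposure would therefore persist through much of the gap.

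**The case against.** The conflict depends on how 6.1.3.2 is read. Its last paragraph makes MAD entry conditional on favorable IDMC advice, so its even-if clause may cover only subjects still in the trial whose MAD cohort does not open. On that reading nothing collides, and 7.11.1 simply ends the visits. On the other reading, supported by 3.1.1 making withdrawal the exception to MAD participation, the visits are already requested. This stands: the text is unsettled, not plainly contradictory.

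Both paths are voluntary. Section 6.1.3.2 only asks subjects to attend, and 4.5 encourages the discontinuation assessments, safety evaluations in particular. This also stands.

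A reader might infer three stronger points that the documents do not support:

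- **That 4.5 also forces the subject out.** It does not; it lists reasons that may apply. Only 7.11.1 is mandatory.
- **That these subjects are left without follow-up.** Every trigger is related to IMP by definition, so 7.10 follows an ongoing one until stable. Section 7.2 calls for prompt examination and retesting of platelet, liver and kidney signals, 6.1 allows unscheduled safety samples, and the IDMC convenes within 3 business days. Section 7.10, however, covers ongoing events. New ones depend on the remaining visits, and after the trial 7.7 asks for an SAE report only if the event may be causal and the investigator learns of it.
- **That the by-dose adverse event comparison is biased.** Nothing shows this. Under SAP 6.14.1 the treatment-emergent window closes 28 days after the last dose. For a subject dosed only on Day 1, events starting from Day 29 fall outside the TEAE tables, though they would still be listed.

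**Conclusion.** The point holds as a gap in safety follow-up wording, of low severity. Section 7.11.1 read literally removes up to 7 scheduled visits from Day 29, with 7 platelet counts and at least 4 ALT/AST tests, and leaves at most 2 of each. These are maxima for a trigger before Day 29; the loss shrinks with later triggers and is at most 1 platelet count for a trigger after Day 71. What is reduced is scheduled detection of new events, not follow-up of the event that triggered the rule.

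The 62-to-83-day gap rests on an assumed date for the early-discontinuation visit and on 3 months being 90 days. The documents do not say how many of the approximately 18 subjects would meet a trigger in this window. MAD is barely affected, because it has no post-dose visit series comparable to the SAD washout. No planned analysis changes. The SAP records that the study was terminated early, so the wording matters chiefly if it is reused.

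**What to change.** In 7.11.1, replace the requirement to discontinue the trial with two statements. The subject permanently stops IMP. Unless consent is withdrawn, a SAD subject is still asked to complete the remaining SAD safety visits to Week 17 under 6.1.3.2, with the early-discontinuation and 3-month assessments combined with those visits where possible. A MAD subject follows 6.1.5 and 6.1.4.

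Then align four other texts:

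- 4.5, so that a pausing rule is a reason for withdrawal from IMP;
- the early-discontinuation notes under both SAD schedules, which otherwise still describe only the Week 25 and 3-month path;
- 3.1.2, so that replacement is triggered by permanent withdrawal from IMP and still works.

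The cost is five short edits, with no new visit type and no SAP change. The downside is burden on a subject who may be unwell. An event on Day 1 leaves up to 12 already-scheduled contacts (Days 2, 3, 8, 11 and 15 make 5, plus 7 from Day 29; Day 11 is a laboratory sample only). An event after Day 29 leaves at most 6. The subject may decline any of them.

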7.11.2 Individual Treatment Interruptions and Dose Adjustments

As thrombocytopenia is a known side effect of ASOs, it is important to always check that the subject has a normal platelet count before dosing. If a decreased platelet count is detected (i.e. value $<$ lower limit of normal [LLN]), a retest should be performed immediately in the local laboratory. If the retest confirms a platelet count value $<$ LLN, the subject may NOT be dosed.

Treatment interruptions will be considered in the event of any suspicion of vasculitis or in the event of any of the following situations that may occur, considered related to IMP:

- Platelet count is between 75,000 and 150,000/ μ L; in that case the subject can be dosed as soon as the platelet count has returned to a value $>$ LLN and dosing can resume at the same dose.
- Platelet count is $<$ 75,000/ μ L; in that case the subject can be dosed as soon as the platelet has returned to a value $>$ LLN, however dosing should be resumed at 50% of the previous dose.
- Platelet count is $<$ LLN and a previous dose interruption had taken place because of decreased platelet values; in this case, the medical monitor should be contacted to discuss possible additional treatment interruptions and/or dose adjustments.

Furthermore, treatment interruptions and/or dose adjustments for an individual subject should be considered in the event of any of the following events:

- Elevation of AST and/or ALT $>$ 3 \times ULN
- Elevation of bilirubin $>$ 2 \times ULN
- Elevation of ALP $>$ 1.5 \times ULN
- Elevation of ALT and/or AST in temporal association with nausea, vomiting, anorexia, abdominal pain, or fatigue
- Clinically significant deteriorating kidney function during treatment
- Any other clinically significant deterioration during treatment considered related to IMP.

In these instances, the medical monitor should be contacted to discuss potential treatment interruptions and/or dose adjustments.

In case a treatment interruption is needed for any safety reason for more than 4 consecutive weeks, or if there is a second treatment interruption on the initial or reduced dose level, the site should always contact the medical monitor to determine the best strategy for the subject, considering the individual risk-benefit ratio.

Note: If treatment is interrupted for circumstances other than safety reasons, the site should also contact the medical monitor to determine whether it is allowed or possible to restart treatment, and if so, at what dose.

